6.4. ANALYSIS VISIT WINDOWS

Table 3 shows how data will be mapped to analysis visits prior to selection of records for analysis. All post-baseline visits, including unscheduled and early termination visits, will be mapped. After mapping the data to the analysis visits, the following rules will apply unless other handling is specified for a particular analysis.

- If multiple records are available within a single analysis visit window, the record closest to the planned assessment day will be selected for analysis.

- If 2 records are equidistant from the target day, then the later record will be selected.
- If a subject has no record in an analysis window, the subject will be considered missing at that visit.

Table 3 Analysis Visit Windows

Data type	Study Day Window	Scheduled day	Scheduled Visit/Week
Body Weight, HbA _{1c} , Fasting Plasma Glucose, Lab data (including Lipids), EQ-5D-3L	Day 2 - 63	Day 42	Visit 9/Week 6
	Day 64 - 125	Day 84	Visit 10/Week 12
	Day 126 - 209	Day 168	Visit 11/Week 24
	Day 210 - 293	Day 252	Visit 12/Week 36
	Day 294 - 377	Day 336	Visit 13/Week 48
	Day 378 - 461	Day 420	Visit 14/Week 60
	Day 462 - 587	Day 504	Visit 15/Week 72
	> 587	Day 672	Visit 17/Week 96
Vital signs (except for height and weight)	Day 2 - 21	Day 14	Visit 7/Week 2
	Day 22 - 35	Day 28	Visit 8/Week 4
	Day 36 - 63	Day 42	Visit 9/Week 6
	Day 64 - 125	Day 84	Visit 10/Week 12
	Day 126 - 209	Day 168	Visit 11/Week 24
	Day 210 - 293	Day 252	Visit 12/Week 36
	Day 294 - 377	Day 336	Visit 13/Week 48
	Day 378 - 461	Day 420	Visit 14/Week 60
	Day 462 - 587	Day 504	Visit 15/Week 72
	> 587	Day 672	Visit 17/Week 96
ECG	Day 2 - 294	Day 168	Visit 11/Week 24
	Day 295 - 546	Day 420	Visit 14/Week 60
	> 546	Day 672	Visit 17/Week 96

* Week 96 is the end of treatment visit for those subjects completing the study per protocol. For endpoint of lab and vital sign, the first collection after assigned Week 96 and > 7 days from Week 96 visit will be considered as Week 98 visit.

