8.1.1. Primary Efficacy Analysis

Let $\mu_{\text{bexagliflozin}}$ and $\mu_{\text{glimepiride}}$ represent the mean changes from baseline in HbA_{1c} at Week 60 for bexagliflozin and comparator groups, respectively. The following hypotheses will be tested:

$$H_0: \mu_{\text{bexagliflozin}} - \mu_{\text{glimepiride}} > \delta \text{ versus}$$

$$H_1: \mu_{\text{bexagliflozin}} - \mu_{\text{glimepiride}} \leq \delta$$

Non-inferiority margin δ is chosen to be 0.35% using clinical judgment, with reference to relevant regulatory guidance, and justified by published glimepiride efficacy study (Charpentier et al. 2001).

This hypothesis will be tested based on ITT analysis set. Missing data will be imputed via multiple imputations, following which the MMRM will be repeated on the complete datasets with results combined across complete datasets using standard multiple imputations techniques; HbA_{1c} values collected after the start of rescue medication will not be excluded. A pattern-mixture model will be used to explore the impact of the missing data. Imputation will be conducted within each treatment arm and subgroup (treatment completer vs. treatment terminated early) under the assumption that non-adherent subjects with missing data will follow the same trajectory of non-adherent subjects with values observed. All efforts will be made to retain subjects in the study. If treatment is discontinued, subjects are encouraged to remain in the study and complete all scheduled visits, including final follow-up visit. However, with all efforts, insufficient values may be available for reliable imputation. This analysis will be performed only if $\geq 3\%$ (approximately 6) of subjects in each treatment arm completed scheduled week 60 visit after treatment is stopped. This number is chosen to allow sufficient data to establish a regression model for imputation. For this analysis, the following three-step approach outlined below will be used:

1. Non-monotone (intermediate visits) missing data will be imputed first using the Monte Carlo Markov Chain (MCMC) method under the MAR assumption in all

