treatment arms (using the MCMC statement in PROC MI). Multiple chains option (CHAIN=MULTIPLE option in the MCMC statement of PROC MI) will be used. For the non-monotone imputation of the HbA_{1c} missing data, a multivariate normal model will be used including variables for the HbA_{1c} at baseline and all post-baseline visits within each treatment group. Five hundred imputed datasets will be generated.

2. After the non-monotone missing data have been imputed, the remaining monotone missing data will be imputed within each treatment arm and subgroup, defined by whether subject completed 60 week of study treatment, using regression approach. The predictors for the regression imputation model at any time point will be region, treatment background (metformin only or metformin and OHA), baseline eGRF (≥ 90 or < 90 ml/min/1.73 m²), and HbA_{1c} at all previous time points, including baseline. Imputations will be performed using a sequence of regression-based imputations (using PROC MI statement MONOTONE REG) at each post-baseline time point.
3. Imputed data in each of the multiple imputed datasets will be analyzed using a mixed model repeated measures (MMRM) approach. The MMRM model will include region, terms for treatment background (metformin only or metformin and OHA), baseline eGRF (≥ 90 or < 90 ml/min/1.73 m²), treatment, visit, treatment-by-visit interaction, and the baseline HbA_{1c} value, as a fixed effect covariate. The analysis will evaluate the mean change from baseline in HbA_{1c} over the 60-week double blind treatment period. An unstructured covariance will be used to model the within subject correlation. The Kenward Roger approximation will be used to estimate denominator degrees of freedom. If the model with the unstructured covariance structure does not converge, an autoregressive(1) covariance structure will be used. HbA_{1c} values obtained after the start of rescue medication will not be excluded from the analysis. The treatment and treatment by visit interaction terms allow for comparisons of the treatment groups at each visit, and over week 12 to week 60. Least squares (LS) mean treatment differences between the bexagliflozin group and the placebo group at week 60 will be estimated from the model. The LS mean results from all imputed datasets will be combined using the Rubin's combination rule (PROC MIANALYZE).

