If no sufficient week 60 values from treatment discontinued subjects are available for imputation, MMRM analysis as in step 3 will be performed using all available data.

Sample SAS code will be provided in Appendix.

In non-inferiority analysis, a CI is calculated to estimate the range of values in which the treatment difference is likely to lie. This CI is used to provide the basis for drawing the study's conclusions. In this specific test, if the 95% CI lies below the specified non-inferiority margin 0.35%, the results would lead to a conclusion of non-inferiority of

bexagliflozin treatment to glimepiride treatment. Lower HbA_{1c} value indicates improvement on subject diabetes condition. Larger decrease would indicate better treatment effect of bexagliflozin compared to glimepiride. Hence, superiority of bexagliflozin group over glimepiride group at week 60 in HbA_{1c} change from baseline will be declared if the upper bound of 95% CI is less than 0.

Descriptive statistics (n, mean, Q1, median, Q3, SD, minimum, and maximum) will be reported by treatment group and visit, along with the least squares means, differences between LS means, a 2-sided 95% confidence interval for each difference, p-values from the model effects. In addition, the LS means with standard errors of the change from baseline over time and difference between treatment groups with 95% will be presented graphically for the ITT population.

For supportive analyses, regardless of having sufficient week 24 values from treatment discontinued subjects are available for imputation or not, MMRM analysis will be performed using all available data. The primary efficacy endpoint will also be analyzed with all observed available data using MMRM method for the PP analysis set.

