13. CHANGE FROM ANALYSIS PLANNED IN PROTOCOL

In all analysis models, continuous HbA_{1c} at baseline is used as fixed effect, in place of randomization stratification factor of HbA_{1c} group at baseline. In all models, eGFR at baseline category is used as fixed effect, in place of randomization stratification factor of eGFR at screening.

Primary analysis of the primary endpoint was MMRM using available data in the protocol. In SAP, a “retrieved dropout” analysis is used for handling missing data is used as primary analysis if data allows. Retrieve dropouts are subjects who discontinued treatment but still had their efficacy measurements at the planned visit. Sensitivity analysis of LOCF is planned in the protocol, but removed in SAP since LOCF does not add more information on sensitivity in addition to tipping point analysis.

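### The 3% (about 6 per arm) trigger for the primary retrieved-dropout imputation is too low for the week-60 regression it is meant to support, which has 9 coefficients

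*SAP*

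**What the plan says.** SAP 8.1.1 imputes missing HbA1c separately by arm and by whether the subject completed treatment, so that off-treatment subjects with missing values follow off-treatment subjects with observed values. The analysis is run only if a threshold is met: at least 3% of the arm, glossed as "approximately 6) of subjects in each treatment arm completed scheduled week 60 visit after treatment is stopped". The reason given is: "This number is chosen to allow sufficient data to establish a regression model for imputation".

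Step 2 of the same section imputes the monotone missing values by sequential linear regression within arm and subgroup. The predictors are region, treatment background, eGFR class and HbA1c "at all previous time points, including baseline. Imputations will be performed using a sequence of regression-based imputations".

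Three statements bear on what happens when data are thin. Before the threshold: "However, with all efforts, insufficient values may be available for reliable imputation". After step 3: "If no sufficient week 60 values from treatment discontinued subjects are available for imputation, MMRM analysis as in step 3 will be performed" on all available data. In SAP 13, the retrieved-dropout approach "is used for handling missing data is used as primary analysis if data allows". The supportive MMRM is then promised "regardless of having sufficient week 24 values from treatment discontinued subjects are available for imputation or not", which names a different week from the fallback sentence.

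**The concern.** The threshold decides which analysis of the primary endpoint is primary, and its stated justification is that it gives enough data to fit the imputation regression. The donors for the week-60 regression are the early-terminated subjects in one arm who have a week-60 HbA1c. Completers and the other arm contribute nothing to that fit. If the donor count can meet the threshold and still fall below the number of coefficients, the threshold does not do what it was chosen to do.

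The count is per arm, and SAP 2.2 opens the treatment codes only after database lock. Any decision the text leaves open would therefore be taken with treatment known. Examples are dropping predictors, accepting a fit on almost no residual information, or moving to the MMRM.

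**Working it through.** **The plan's own figures.** SAP 3.8 gives 172 per arm and 18% drop-out: 172 / (1 − 0.18) = 209.8, so 210 per arm. Three per cent of 210 is 6.3, which matches the SAP's approximate 6. Taken strictly, 6/210 = 2.86% fails and 7/210 = 3.33% is the first count that passes.

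**Coefficients in the step-2 model.** Inputs:
- Region has two levels, Europe and North America (SAP 6.5): 1 coefficient.
- Treatment background has two levels: 1.
- eGFR class has two levels: 1.
- HbA1c is measured at Visit V5 (baseline) and at weeks 12, 24, 36, 48 and 60 (Protocol Appendix 2; SAP Table 1): one coefficient for each earlier time point.
- Intercept: 1.

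Coefficients = 1 + 3 + (number of earlier HbA1c time points, including baseline). A regression imputation that draws the residual variance needs at least one residual degree of freedom, so minimum donors = coefficients + 1.

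| Imputed visit | Earlier HbA1c values | Coefficients | Minimum donors |
|---|---|---|---|
| Week 12 | 1 | 5 | 6 |
| Week 24 | 2 | 6 | 7 |
| Week 36 | 3 | 7 | 8 |
| Week 48 | 4 | 8 | 9 |
| Week 60 | 5 | 9 | 10 |

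In a monotone pattern the number of donors cannot rise from one visit to the next, while the number of coefficients does. Week 60 is therefore the binding visit. Step 1 fills gaps at intermediate visits but adds no week-60 donor.

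**Residual degrees of freedom at week 60 (donors − 9).**
- 6, 7 and 8 donors: −3, −2 and −1. There are fewer rows than coefficients, so the model is not identified.
- 9 donors: 0. The fit is exact and leaves no residual variance to draw from.
- 10 donors (10/210 = 4.8%): 1.

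**Whether 10 is enough.** In the usual normal-model draw, the residual SD used for imputation is the estimate times √(df / χ²), with χ² on df degrees of freedom. Its 95% range, as a multiple of the estimate, is:
- 10 donors (1 df): 0.45 to 32
- 11 donors (2 df): 0.52 to 6.3
- 12 donors (3 df): 0.57 to 3.7
- 20 donors (11 df): 0.71 to 1.7

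Ten is the point at which software can return an answer. It is not a point at which the imputation is reliable.

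**Week 6.** SAP Table 3 gives HbA1c a week-6 window although no week-6 HbA1c is scheduled. Counting that visit would add one coefficient and raise the minimum to 11.

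**The case against.** The strongest reply is that a fallback exists. The 3% rule is worded as a necessary condition, the sentence before it speaks of reliable imputation, and both the fallback sentence in 8.1.1 and SAP 13 allow for data that do not suffice. On an ordinary reading, a regression that cannot be fitted goes to the available-data MMRM. That reading is fair, so the stronger inference that the plan has no route out does not stand. What remains is that 3% is the only test of sufficiency the SAP states. Seven to 9 donors pass it, and so does a fit on 1 to 3 degrees of freedom, from which no sentence directs the analyst away.

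Second, the trigger count is not the donor count. SAP 6.4 says "All post-baseline visits, including unscheduled and early termination visits, will be mapped", and the week-60 window is Day 378 to 461. An exit visit two weeks after the last dose (Protocol 7.4.1) falls in that window if treatment stopped from Day 364 (378 − 14), and an End of Treatment visit (Protocol 7.5) if it stopped from Day 378. Such values may add donors. However, the trigger counts only scheduled week-60 visits completed after stopping, and the plan does not rely on the extra values.

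Third, the SAP promises sample SAS code in an appendix that was not available for review. A shorter predictor list there cannot be ruled out. The body of the SAP would still need to agree with it.

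A reader might also infer that a shortfall is likely. The documents do not support that, because none gives an expected number of retrieved subjects. If the 18% covers everyone who stops early (0.18 × 210 = about 38 per arm), 10 donors means retrieving about 26% of them (10/38). That is a scale, not a probability.

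**Conclusion.** The point holds. The stated threshold of about 6 per arm (strictly 7 of 210) is too small for the 9-coefficient week-60 regression in step 2. At least 10 donors per arm are needed for one residual degree of freedom, and more for a usable fit. This rests on the predictor list as written, two regions, and the scheduled HbA1c visits. It matters only if an arm ends with few donors, and the chance of that is unknown.

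The consequence is limited. A fit on very few degrees of freedom gives a very wide interval, and an unfittable one leaves the primary analysis to be settled after unblinding. It would be tempting to conclude that non-inferiority could be falsely declared. The documents do not support this: unstable imputation inflates the combined variance, and the available-data MMRM is reported in any case. The reference to week 24 in the supportive-analysis sentence looks like a slip, but it blurs the sufficiency test further, because the same model has only 6 coefficients at that visit.

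**What to change.** In SAP 8.1.1, before unblinding:

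- **Make the trigger and the model agree.** One way is to cut the step-2 predictors for the early-terminated subgroup to baseline HbA1c and the immediately preceding HbA1c. That is 3 coefficients with the intercept, so 7 donors would leave 4 residual degrees of freedom. The other way is to set the trigger as a per-arm donor count comfortably above the number of coefficients, which means more than 10 if the full model is kept. The two can be combined. The exact count is for the sponsor to choose and justify.
- **Close the gap.** State that the available-data MMRM is primary unless both arms meet the count and the imputation regression can be fitted.
- **Correct the wording.** Change week 24 to week 60 in the supportive-analysis sentence, and check that the appendix code matches.

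The cost is SAP text and imputation code. With a higher count, the MMRM fallback is used somewhat more often, and the off-treatment assumption then does not enter the primary estimate. With the shorter list, region, background and eGFR class leave the imputation model for this subgroup, though they stay in the step-3 MMRM.

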9.5.2 Statistical Methods for Primary Analyses

For the primary endpoint, the treatment difference will be examined by using a mixed model repeated measures (MMRM) analysis of covariance model (ANCOVA). The model will include treatment, visit, treatment-by-visit interaction and randomization stratification factors as the fixed effects terms and the baseline HbA1c value as a fixed effect covariate. Least squares mean treatment differences between the bexagliflozin group and the comparator group at week 60 will be estimated from the model. An unstructured covariance will be used to model the within-subject correlation. If the model with the unstructured covariance structure does not converge, an autoregressive(1) covariance structure will be used.

HbA1c values obtained after the start of rescue medication will not be excluded in the analysis. These analyses will be conducted on both ITT (primary) and PP analysis sets, and conclusions can be considered more robust when both approaches support the non-inferiority of the treatment.

In non-inferiority analysis, a CI is calculated to estimate the range of values in which the treatment difference is likely to lie. This CI is used to provide the basis for drawing the study's conclusions. In this specific test, if the 95% CI lies below the specified non-inferiority margin 0.35%, the results would lead to a conclusion of non-inferiority of bexagliflozin treatment to glimepiride treatment. Superiority of bexagliflozin group over

glimepiride group at week 60 in HbA1c change from baseline will be declared if the upper bound of 95% CI is less than 0.

Sensitivity analyses will also be performed as the following, and these analyses will be conducted for ITT and PP analysis sets.

1. Missing data will be imputed via multiple imputations, following which the MMRM will be repeated on the complete datasets with results combined across complete datasets using standard MI techniques; HbA1c values collected after the start of rescue medication will not be excluded.
2. Missing data will be imputed via LOCF, following which the MMRM will be repeated; HbA1c values collected after the start of rescue medication will be considered missing.
3. HbA1c values collected after the start of rescue medication will be considered missing, and the MMRM analyses will be re-performed.

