3.8. DETERMINATION OF SAMPLE SIZE

An approximate total of 420 subjects will be randomized and equally allocated to receive:

- bexagliflozin tablets, 20 mg and glimepiride, placebo capsules (referred to as bexagliflozin group in this document)
- bexagliflozin tablets, placebo and glimepiride capsules, 2 mg, 4 mg, or 6 mg (referred to as glimepiride group in this document).

The sample size calculation for this study is based on a two group t-test with a one-sided significance at the 0.025 level and the following assumptions:

- The non-inferiority limit (margin) for mean change from baseline to week 60 in HbA_{1c} comparing bexagliflozin group to glimepiride group will be 0.35%
- The standard deviation for the change from baseline to week 60 in HbA_{1c} for bexagliflozin group and glimepiride group will be 1.0%

Under the above assumptions, an estimated sample size of 172 subjects is needed in each treatment arm to determine non-inferiority of bexagliflozin to glimepiride with respect to change in HbA_{1c} at week 60 from baseline. This estimation is based on a one-sided t-test with 90% power at a 0.025 level of significance. A sample size of 210 per arm has been selected to account for approximate 18% drop-out rate and to allow adequate safety evaluation. The total sample size for this study will be 420 subjects.

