3.9. TREATMENT ASSIGNMENT & BLINDING

3.9.1. Treatment Assignment

The study will be conducted at multiple investigative sites and will likely involve various numbers of subjects at each site. The study will have a competitive enrollment but the number of randomized subjects from each site will be capped at 40. Activation of investigational sites will be centrally controlled by an Interactive Web Response System (IWRS). Subject randomization will be deactivated for all sites when the planned number of subjects is met. However, if a potential subject is in wash-out already and wishes to continue with the study, the subject will be allowed to continue and, if eligible, to be randomized.

Eligible subjects who have completed the wash-out of oral hypoglycemic agent other than metformin and have met all study inclusion/exclusion requirements are to be randomized in a 1:1 ratio to receive active bexagliflozin with placebo glimepiride or active glimepiride with placebo bexagliflozin. Subjects will be assigned to treatment groups in sequential order as they qualify for the study. Randomization will be stratified according to baseline (Visit V5) HbA_{1c} (< 8.5% or ≥ 8.5%), treatment background

(metformin-only or metformin-and-OHA), and Visit V5 eGFR (≥ 90 or < 90 and ≥ 60 mL/min/1.73 m²).

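### The primary MMRM holds one baseline-HbA1c slope across weeks 12 to 60; adding baseline-by-visit costs four parameters and may modestly narrow the week-60 confidence interval

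*SAP*

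**What the plan says.** SAP 8.1.1 step 3 lists region, treatment background and baseline eGFR category, then "treatment, visit, treatment-by-visit interaction, and the baseline HbA_{1c} value, as a fixed effect covariate". The covariance is unstructured, with AR(1) as fallback. Protocol 9.5.2 has the same structure: "The model will include treatment, visit, treatment-by-visit interaction and randomization stratification factors as the fixed effects terms and the baseline HbA1c value". Neither document crosses baseline HbA1c with visit. SAP section 13 replaces the HbA1c stratum by continuous baseline HbA1c but adds no interaction.

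The step 3 model also serves the available-data fallback in SAP 8.1.1 and the tipping-point analysis in SAP 8.1.2. The PP analysis in SAP 8.1.1 is likewise an MMRM on observed data.

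Step 2 works differently. It imputes monotone missing values by a separate regression at each visit, with baseline and all earlier HbA1c values as predictors, so there the baseline slope is free to differ by visit.

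**The concern.** Non-inferiority is judged on the week-60 difference alone. Under an unstructured covariance, a single baseline slope settles at a precision-weighted average of the five visit-specific slopes. If the week-60 slope is not equal to that average, part of the baseline variation stays in the week-60 residual. The interval compared with the 0.35 margin is then somewhat wider than a model with visit-specific slopes would give. The direction of the drift does not matter; only the gap between the week-60 slope and the average does.

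What is at stake is some precision at the decision visit. The analysis model is also more restrictive than the imputation model that feeds it.

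**Working it through.** **1. The plan's own figure.** Inputs from SAP 3.8 and 3.9.1:
- margin: "comparing bexagliflozin group to glimepiride group will be 0.35"
- SD: "for bexagliflozin group and glimepiride group will be 1.0"
- test: "This estimation is based on a one-sided t-test with 90% power at a 0.025 level of significance"
- allocation: "are to be randomized in a 1:1 ratio to receive active bexagliflozin"

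The true difference is not stated and is taken as 0. Then n per arm = 2(1.960 + 1.282)² × 1.0² / 0.35² = 171.5, so 172, which agrees with "an estimated sample size of 172 subjects is needed in each treatment arm". Noncentral-t power at 172 per arm is 89.9%. Next, 172 / 0.82 = 209.8, so 210, which agrees with "A sample size of 210 per arm has been selected to account for approximate 18% drop-out rate". The sample size uses an SD that is not adjusted for baseline.

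**2. Formula.** Let b be the vector of true visit slopes, S the residual covariance, sB the baseline SD and s60 the week-60 residual SD. In large samples:
- fitted common slope: bc = 1'S⁻¹b / 1'S⁻¹1
- week-60 residual variance, common slope: s60² + (b60 − bc)² sB²
- week-60 residual variance, baseline-by-visit: s60²
- CI width ratio, common / by-visit: √[1 + (b60 − bc)² sB² / s60²]

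**3. Assumed inputs.** The documents give only the eligible HbA1c range. Assumed:
- sB = 0.85 (range 0.70 to 1.00)
- slopes linear over the five visits, except in the last row of the table
- residual SD rising to s60 from 75% of it
- residual correlation 0.3 + 0.7 × 0.7^lag (alternative 0.6^lag)
- marginal week-60 SD held at the SAP's 1.0, so s60 = √(1 − b60² sB²)

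Half-width = 1.96 × SD × √(2/172).

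**4. Worked case, slope −0.20 to −0.60.** s60 = √(1 − 0.36 × 0.7225) = 0.860 and bc = −0.306. The ratio is √[1 + 0.294² × 0.7225 / 0.7396] = 1.041. The half-width goes from 0.1893 to 0.1818.

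**5. Results at sB = 0.85.**

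| Slope, week 12 to 60 | bc | s60 | Half-width, common → by-visit | Narrower by |
|---|---|---|---|---|
| −0.40 constant | −0.400 | 0.940 | 0.1988 → 0.1988 | 0 |
| −0.35 to −0.45 | −0.376 | 0.924 | 0.1957 → 0.1953 | 0.2% |
| −0.30 to −0.50 | −0.353 | 0.905 | 0.1931 → 0.1913 | 0.9% |
| −0.20 to −0.60 | −0.306 | 0.860 | 0.1893 → 0.1818 | 4.0% |
| −0.50 to −0.30 | −0.447 | 0.967 | 0.2061 → 0.2044 | 0.8% |
| −0.60 to −0.20 | −0.494 | 0.985 | 0.2149 → 0.2083 | 3.1% |
| −0.5, −0.4, −0.3, −0.4, −0.45 | −0.460 | 0.924 | 0.1953 → 0.1953 | nil |

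Over sB 0.70 to 1.00 and both correlation patterns, modest drift (rows 2, 3 and 5) gives 0.1% to 1.4%. Strong steepening (row 4) gives 1.8% to 6.2%, and strong weakening (row 6) gives 1.6% to 4.2%.

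**6. A second set of assumptions.** Take sB 0.85, residual SD rising from 0.65 to 0.90 and correlation 0.8^lag. The week-60 variance ratios (common / by-visit) are 1.011, 1.045 and 1.079 for slopes −0.40 to −0.55, −0.30 to −0.60 and −0.25 to −0.65. Their square roots, the CI width ratios, are 1.006, 1.022 and 1.039. With a constant residual SD of 0.8 the variance ratios fall to 1.006, 1.025 and 1.045.

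**7. Simulation check.** Unstructured MMRM, 400 trials per setting. The ratio of week-60 standard errors (by-visit / common), with 172 complete per arm and then 210 per arm with 18% dropout, was:
- constant slope: 1.000 and 0.9998
- −0.35 to −0.45: 0.998 in both
- −0.30 to −0.50: 0.991 and 0.990
- −0.20 to −0.60: 0.961 and 0.957
- −0.50 to −0.30: 0.992 with complete data; the dropout version did not finish

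The mean error of the common-slope estimate never exceeded 0.006 in absolute size. With a standard error near 0.1, Monte Carlo error is about 0.1/√400 = 0.005, so no bias is visible.

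**The case against.** **No premise in the documents.** A reader might infer that the baseline slope usually steepens with time. No passage says so, and none gives a slope. The first modelled HbA1c is at week 12, after glimepiride titration closes at week 6, so a two-fold change between weeks 12 and 60 is purely an assumption. This stands. The point does not need steepening, since weakening also widens the interval, but it does need some drift.

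**Stratified randomization.** Randomization is stratified on V5 HbA1c at 8.5% (SAP 3.9.1), which limits chance baseline imbalance. In 20,000 simulated trials per setting under the step 6 slopes (assumed mean baseline 8.2), stratification cut the excess empirical week-60 variance from 1.0% to 0.3%, from 4.4% to 2.0%, and from 7.9% to 3.1%. This stands for true precision. The reported interval was still wider by about 0.4%, 2.1% and 3.8%, because the common-slope standard error does not use the stratification.

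**Subject equivalents.** A reader might turn variance excesses of 4% and 8% into 14 to 28 of 344 evaluable subjects (0.04 × 344 and 0.08 × 344). That takes only scenarios in which the slope at least doubles, and it ignores stratification and imputation. It should not be used.

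**Power.** A reader might infer that the trial is underpowered. The sample size already uses an unadjusted SD, so baseline adjustment is a bonus. For sB 0.85 the common-slope power is 95.1% (by-visit 96.4%) with the slope going from −0.20 to −0.60. It falls just below the planned 90% only when the slope weakens sharply: 88.9% against 90.7% for −0.60 to −0.20.

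**Different primary analysis.** If data allow, the primary analysis combines 500 retrieved-dropout imputations, which were not simulated here. Between-imputation variance would dilute the relative gain. This stands.

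**A legitimate prespecified choice.** Protocol and SAP agree on the common slope, and the SAS appendix was not available. This also stands: the plan contains no error here, only a cheap improvement left out.

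**Conclusion.** The point holds as a low-priority precision refinement. The common-slope model is valid, and a reading that the week-60 estimate is biased or the non-inferiority test unsound is not supported.

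The benefit lies between nothing and a few percent of interval width: nil for a constant slope, about 1% or less for modest drift (1.4% at the largest assumed baseline SD), and about 2-4%, at most about 6%, for a change of two-fold or more. In absolute terms the strong-steepening case at sB 0.85 removes 0.1893 − 0.1818 = 0.0075 from the half-width, against a margin of 0.35. All of this rests on assumed baseline SD, slopes and correlations. Imputation would make the realised gain smaller.

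The case for acting is that the cost is negligible, the direction of drift need not be known, and the analysis model would then allow what the imputation model already allows.

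**What to change.** Before unblinding, add baseline HbA1c-by-visit to the model in SAP 8.1.1 step 3, and so to the available-data, PP and tipping-point MMRMs. List the change in SAP section 13 and make the appendix SAS code match. If that code already contains the term, the SAP text should say so.

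The cost is four fixed-effect parameters (five visits less one) against about 344 evaluable subjects. It needs no new data or patients, and no loss was measurable when the slope was constant.

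A matching term for body weight, SBP and FPG (SAP 8.2.1, 8.2.2, 8.3.1) is optional and was not evaluated. Up to week 60 it costs five parameters for weight (six post-baseline visits) and seven for SBP (eight visits). The case is weakest in the smaller subgroup with baseline SBP ≥ 140 mmHg.
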